13. MANAGEMENT OF TOXICITIES AND COMPLICATIONS

13.A. Toxicity Grading

Toxicity grading will be evaluated according to the current guidelines in NCI Common Toxicity Criteria version 4.0.⁷⁷ The full text of the NCI CTCAE is available online at: <http://evs.nci.nih.gov/ftp1/CTCAE/About.html>.

13.B. Regimen Related Toxicity

If the patient develops excessive Toxicity attributable to one or more component of the regimen, the patient will not receive additional study treatment and a treatment of corticosteroids will be given, if clinically indicated (please refer to **Section 13.C**). Excessive toxicity will be considered when a non-pre-existing Grade 3 or higher toxicity develops after the start of treatment with the following exceptions:

13.B.1. Expected toxicities attributable to anti-PD-L1 (Avelumab) infusions and considered exceptions to criteria for discontinuation include:

1. Infusion-related reactions (see **Section 13.C** for management):
 - i. Transient (\leq 6 hours) Grade 3 CRS, flu-like symptoms or fever, which is controlled with medical management.
 - ii. Transient (\leq 24 hours) Grade 3 fatigue, local reactions, headaches, nausea, emesis that resolved to \leq Grade 1.
 - iii. Single laboratory values out of normal (excluding Grade \geq 3 liver function tests increase) that are unlikely related to Avelumab according to the investigator, do not have a clinical correlate, and resolve to \leq Grade 1 within 7 days with adequate medical management.
 - iv. Urticaria lesions responding to antihistaminics (Grade 2)
 - v. Allergic reaction (flushing or rash) responding to antihistaminic treatment (Grade 2).
2. Tumor flare phenomenon defined as local pain, irritation, or rash localized at sites of known or suspected tumor.

3. Tumor-lysis syndrome: If symptoms of tumor lysis occur after the Avelumab infusions they will be managed according to best clinical practice (see **Section 13.C.4**). Tumor lysis will not constitute a reason to discontinue the Avelumab infusions.
4. Change in ECOG PS to ≥ 3 that resolved to ≤ 2 within 14 days (infusions should not be given on the following cycle if the ECOG PS is ≥ 3 on the day of the Avelumab administration).

13.B.2. Expected toxicities attributable to **localized radiation** of pre-existing symptomatic metastasis and considered exceptions to criteria for discontinuation include:

- i. Non-life-threatening - diarrhea (i.e. 4-6 stools over baseline stools a day)

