- ii. Target organ inflammatory responses resulting in Grade 3 or 4 toxicities that return to baseline within 4 weeks. For example: elevated lipase and/or amylase after radiation to a pancreatic lesion; or elevated transaminases after radiation to a liver lesion.
- iii. Hyperglycemia (Grade 3) lasting <14 days.
- iv. Dry skin, skin pain, and erythema lasting <14 days.
- v. Single laboratory values out of normal that according to the investigator do not have a clinical correlate and resolve to \leq Grade 1 within 7 days with adequate medical management.

13.B.3. Expected toxicities attributable to **intraleisional IFN β -1B injections** and considered exceptions to criteria for discontinuation include:

- i. Non-life-threatening infections (i.e. absence of hemodynamic compromise requiring pressor support and non-opportunistic infection).
- ii. CRS Grade 3 or less, including but not limited to asthenia, flu-like symptoms, myalgia, lymphopenia, and rigors.
- iii. Target organ inflammatory responses resulting in Grade 3 or 4 toxicities that resolve within 4 weeks. For example: elevated lipase and/or amylase after injection to a pancreatic lesion; or elevated transaminases after injection to a liver lesion.
- iv. Single laboratory values out of normal that according to the investigator do not have a clinical correlate and resolve to \leq Grade 1 within 7 days with adequate medical management.

13.B.4. Expected toxicities attributable to **T-cell infusions** and considered exceptions to criteria for discontinuation include:

- i. CRS Grade 3 or less, including but not limited to asthenia, flu-like symptoms, myalgia, lymphopenia, and rigors.
- ii. Skin rash or erythroderma (Grade 3 toxicity) lasting for <7 days.

- iii. Hypoxemia requiring continuous oxygen <72 hours, but not requiring mechanical ventilation or intubation.
- iv. Fever that resolves within 36 hours of the T-cell infusion.
- v. Lymphopenia (lymphocytes <500) that resolves to baseline levels (pre-therapy) within 4 weeks.
- vi. Single laboratory values out of normal that according to the investigator do not have a clinical correlate and resolve to ≤ Grade 1 within 7 days with adequate medical management.

13.C. Management of Symptoms During Avelumab Infusions

13.C.1. Special precautions

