Patients will also be closely monitored for potential irAEs,^{79,80} which may manifest earliest after weeks of treatment. Such events may consist of persistent rash, diarrhea and colitis, autoimmune hepatitis, arthritis, glomerulonephritis, cardiomyopathy, or uveitis and other inflammatory eye conditions. The spectrum of hypothetical irAEs also includes formation of auto-antibodies like anti-nuclear antibodies (ANAs) or antineutrophil cytoplasmic antibodies (ANCAs). IrAEs will be managed according to **Section 13.E** with steroids.

Suggested management for Grade 2 adverse drug reactions (ADR):

- If a Grade 2 ADR resolves to Grade ≤ 1 by the last day of the current cycle, treatment may continue.
- If a Grade 2 ADR does not resolve to Grade ≤ 1 by the last day of the current cycle, infusions should not be given on the following cycle. If at the end of the following cycle the event has not resolved to Grade 1, the subject should permanently discontinue treatment with a Avelumab ADR (except for hormone insufficiencies, that can be managed by replacement therapy; for these hormone insufficiencies, up to 2 subsequent doses may be omitted).
- Upon the second occurrence of the same Grade 2 ADR (except for hormone insufficiencies that can be managed by replacement therapy) in the same subject, treatment with Avelumab must be permanently discontinued.

13.D. Management of Symptoms During T-Cell Infusion

Immediate reaction to infusion (i.e. defined as those occurring either during the first 24 hours following T-cell infusion) may occur due to release of cytokines from T cells stimulated by the recognition of targets. Mild transient symptoms have been observed with lymphokine-activated killer cell (LAK) and TIL cell infusions, and with infusions of antigen-specific T-cell clones (**FHCRC Protocol 2140**).

13.D.1. Milder reactions (i.e. <Grade 3 CTCAE v.4 or less severe than specified below) would include symptoms such as:

- Fever, chills, fatigue.
- Dyspnea, chest tightness, or myalgia,
- Alteration in vital signs such as:
 - Lowering of blood pressure, but with systolic BP ≥ 90 mm Hg, or ≤ 20 mm Hg below baseline.
 - Tachycardia, but with HR ≤ 130 or ≤ 30 above baseline.
 - Tachypnea, but with RR $\leq 32/\text{min}$ or ≤ 10 above baseline.
 - Hypoxemia, but O₂ saturation $\geq 88\%$ on room air, or $\leq 5\%$ fall from baseline.
 - Skin changes such as erythema, urticaria, or other rash.

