- Growth factors (granulocyte colony stimulating factor or granulocyte macrophage colony stimulating factor). Exception: erythropoietin and darbepoietin alpha may be prescribed at the Investigator's discretion
- Bisphosphonate treatment is not allowed unless it has been initiated more than 14 days prior to receiving the first administration of Avelumab

13.G. Off-study Criteria

A patient's participation on the protocol will be terminated for any of the reasons listed below:

- Progressive disease or development of new metastasis requiring urgent additional drugs (for example chemotherapy)
- The participant withdraws consent
- Patient death
- Occurrence of pregnancy
- Participation in another trial during the treatment duration of this trial
- Occurrence of an exclusion criterion, which is clinically relevant and affects the subject's safety, if discontinuation is considered necessary by the Investigator or Sponsor
- A patient will no longer be eligible to receive additional therapy if the PI or his designee determines that additional T cell and / or avelumab infusions are not in the best interest of the patient
- Occurrence of any non-pre-existing AEs / repetitive Grade 2 AEDRs that are deemed related to the treatment as defined in **Section 13.C.2.**

- Use of a non-permitted concomitant drug such as steroids, or as defined in **Section 13.F.4** for which the predefined consequence is withdrawal from the trial
- The reasons for premature discontinuation must be recorded on the case report form. The patient may re-enter the study after premature discontinuation only by approval of the PI

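### The toxicity bullet in 13.G states no grade for related new adverse events and refers only to 13.C.2, so it conflicts with 13.B, 13.C.5 and 13.D.1 and blurs stopping treatment with leaving the study

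*Combined protocol and SAP*

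**What the plan says.** Section 13.G opens with "A patient's participation on the protocol will be terminated for any of the reasons listed below". One of its reasons is "Occurrence of any non-pre-existing AEs / repetitive Grade 2 AEDRs that are deemed related to the treatment as defined in" Section 13.C.2. The section is operative: under item 2 of Section 11, avelumab runs for 12 months or until the 13.G criteria are met. The last bullet of 13.G allows re-entry after premature discontinuation only if the principal investigator approves.

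Four other places deal with the same events:

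- **13.B** stops further study treatment for excessive toxicity: "Excessive toxicity will be considered when a non-pre-existing Grade 3 or higher toxicity develops after the start of treatment with the following exceptions". The exceptions are listed by component. Under avelumab (13.B.1) they include transient (6 hours or less) "Grade 3 CRS, flu-like symptoms or fever, which is controlled with medical management", and for tumor lysis the text says "Tumor lysis will not constitute a reason to discontinue the Avelumab infusions". Under T-cell infusions (13.B.4) they include "CRS Grade 3 or less, including but not limited to asthenia, flu-like symptoms, myalgia, lymphopenia, and rigors".
- **13.C.2 and its Table 5** cover avelumab infusion-related reactions. Grade 1 slows the infusion. Grade 2 stops it, then allows it to resume at half the rate. Grade 3 or 4 ends avelumab. A second reaction of Grade 2 or higher at the slower rate also ends avelumab.
- **13.C.5** covers delayed and immune-related avelumab toxicity. If a Grade 2 reaction "resolves to Grade ≤ 1 by the last day of the current cycle, treatment may continue". A second occurrence of the same Grade 2 reaction ends avelumab, apart from hormone insufficiencies managed by replacement.
- **13.D.1** handles T-cell infusion reactions below Grade 3, including fever and chills, by slowing the infusion and giving supportive care.

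**The concern.** One event can lead to opposite instructions depending on which section is applied. No clause says which section prevails, and the monitoring guidelines in Section 16 refer to the toxicity section as a whole for individual discontinuation.

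Two things are at stake. The first is delivered treatment: who goes on receiving avelumab and, in Group 2, who reaches the second T-cell infusion. The second is follow-up. 13.B and 13.C.5 stop treatment, whereas 13.G ends participation. The primary efficacy endpoint, time to new metastasis, depends on restaging until a new metastasis occurs (Section 12.D.1). 13.G does not say whether restaging continues for a patient whose participation it has ended.

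**Working it through.** The plan gives no figure to reproduce, so the check is a comparison of texts. The 13.G bullet can be read in two ways.

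- *Literal:* any related adverse event that was not pre-existing ends participation, whatever its grade.
- *Narrow:* the reference to 13.C.2 limits the bullet, so it applies only to avelumab infusion-related reactions, with the grades of that section.

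| Related event | 13.G, literal | 13.G, narrow (13.C.2) | Other section on the same event |
|---|---|---|---|
| Grade 1 avelumab infusion reaction | participation ends | slow the infusion, continue | 13.B: below its threshold |
| First Grade 2 avelumab infusion reaction | participation ends | stop, then resume at half rate | 13.B: below its threshold |
| Transient Grade 3 CRS, flu-like symptoms or fever with avelumab | participation ends | avelumab ends if graded as a Grade 3 infusion reaction | 13.B.1: exempt from discontinuation |
| First Grade 2 avelumab reaction of the 13.C.5 type, resolving within the cycle | participation ends | not covered | 13.C.5: may continue |
| Second occurrence of the same Grade 2 reaction | participation ends | not covered | 13.C.5: avelumab ends, with the hormone exception |
| Grade 2 fever and rigors after T-cell infusion #1 | participation ends | not covered | 13.B.4 and 13.D.1: managed, not a ground to stop |
| Tumor lysis after avelumab | participation ends | not covered | 13.B.1: not a ground to stop avelumab |
| New Grade 3 toxicity with no exception, not an infusion reaction | participation ends | not covered | 13.B: no further study treatment |

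**Literal reading.** The bullet disagrees with at least one specific section in every row except the fifth and the last. In those two it agrees that something stops but differs on what: avelumab or study treatment on one side, participation on the other. It also disagrees with Table 5 of 13.C.2, the section it cites.

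**Narrow reading.** The grades are restored, but only for infusion reactions. Five of the eight rows fall outside the bullet, including the two (fifth and last) where 13.B or 13.C.5 itself requires treatment to stop. The third row remains unresolved between 13.C.2 and 13.B.1.

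**Worked case, Group 2.** Appendix B places T-cell infusion #1 at day 12 and infusion #2 at day 40, so 40 − 12 = 28 days apart. A patient with related Grade 2 fever and rigors after infusion #1 is below the 13.B threshold, is within the 13.B.4 exception and is managed under 13.D.1. The literal bullet would end participation before day 40, and one of the two infusions of the first course would not be given.

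**Weight of one patient.** Section 18 plans 10 patients per group, so one patient whose follow-up stops early is 1/10 = 10% of the data behind that group's median time to new metastasis.

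**The case against.** The strongest reply is that the bullet should be read with its limiting clause. A site that follows the reference finds graded rules in Table 5, and 13.C.2 does contain a rule on repeated reactions of Grade 2 or higher. That stands: a reader might infer that the bullet simply cites the wrong section, and the documents do not support that. The reference fits infusion reactions and is incomplete for everything else. But the narrow reading removes one conflict only by dropping the 13.B and 13.C.5 criteria from the bullet.

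The overlap between 13.C.2 and 13.B.1 can also be argued down. Table 5 describes Grade 3 reactions as prolonged, while 13.B.1 speaks of transient ones, so the two might be meant for different events. The plan does not say so. 13.B.1 lists its exemption under infusion-related reactions and allows up to 6 hours, and 13.C.2 ends avelumab for a Grade 3 reaction at any time.

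Oversight helps as well. Infusions are given at one centre, the principal investigator or a designee reviews patients' progress, and re-entry is possible with approval. These soften the consequence, but case-by-case approval does not replace a consistent rule.

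Three stronger inferences are not supported:

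- *That most patients would be removed.* All 13 of 13 subjects in the avelumab dose-escalation data had a treatment-emergent event, but that count is not limited to related events, and the bullet requires relatedness. Nor is the 30% in Section 18 a comparator: it is a group-level safety benchmark, not an expected rate of individual discontinuation.
- *That Group 2 would lose more patients than Group 1.* Group 2 has an extra agent with its own expected reactions, but no figure in the documents sizes a difference, and both groups receive avelumab and radiation or interferon.
- *That 13.C.5 lets the T-cell patient in the worked case continue.* 13.C.5 concerns avelumab; the support there comes from 13.B.4 and 13.D.1.

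**Conclusion.** The inconsistency is real under both readings and should be corrected. The first half of the 13.G bullet has no grade, its reference is incomplete, and it ends participation where 13.B and 13.C.5 stop treatment. Limiting the bullet through 13.C.2 leaves gaps, together with the open question on Grade 3 infusion reactions.

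The size cannot be stated as a number of patients, because the available text gives no overall rate of related events. What can be stated is the weight of each case: 10% of a group for the primary efficacy endpoint and, for a Group 2 patient removed between days 12 and 40, the second infusion of the first course. The effect on follow-up assumes that ending participation also ends protocol restaging, which 13.G leaves open. The conclusion concerns consistency only and takes no view on which clinical threshold is right.

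**What to change.** At the next amendment:

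1. Reconcile 13.G with 13.B (including its exceptions), 13.C.2, 13.C.5 and 13.D so that one consistent toxicity rule applies. Replace the free-standing first half of the bullet with references to those sections.
2. Reconcile 13.B.1 with 13.C.2 on Grade 3 infusion reactions, saying whether the two describe different events or which text governs.
3. State for each criterion whether meeting it ends study treatment or ends participation, and whether restaging for new metastasis continues afterwards.

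The investigators decide the clinical content. The cost is one rewritten bullet and a clarifying sentence or two, with no new procedures.

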14. TARGETED/PLANNED ENROLLMENT

TARGETED/PLANNED ENROLLMENT: 20 Subjects			
Ethnic Category	Sex/Gender		
	Females	Males	Total
Hispanic or Latino	0	0	0
Not Hispanic or Latino	9	11	20
Ethnic Category: Total of All Subjects *	9	11	20
Racial Categories			
American Indian/Alaska Native	0	0	0
Asian	0	0	0
Native Hawaiian or Other Pacific Islander	0	0	0
Black or African American	0	0	0
White	9	11	20
Racial Categories: Total of All Subjects *	9	11	20

* The “Ethnic Category: Total of All Subjects” must be equal to the “Racial Categories: Total of All”

All racial groups and ethnicities will be included. **These targeted/planned enrollment numbers are based on relative percentages of race/ethnicity reported for MCC cases in the Surveillance, Epidemiology, and End Results (SEER) cancer registry database.**

Sex/Gender

Males	60%
Females	40%

Ethnicity

Hispanic/Latino	3.2%
Not Hispanic/Latino	96.8%

Race

American Indian/Alaska Native	0.18%
Asian	1.4%
Native Hawaiian/Pacific Islander	0.98%
Black/African American	0.84%
White	96.6%

15. GUIDELINES FOR ADVERSE EVENTS REPORTING

15.A. Reporting of Adverse Events

All unexpected and serious AEs which may be due to study treatment or intervention must be reported to the FHCRC Institutional Review Office (IRO) per their current reporting requirements.

All grade ≥ 3 CTCAE v.4 AEs will be collected through 4 weeks after the last T-cell infusion and per section 12.C. Beginning 4 weeks after the last study infusion, only study related toxicities will be collected.

All SAEs that are unexpected and related to study treatment will be reported to the FDA on a MedWatch 3500 reporting form that will be submitted to the FDA within 15 calendar days. The reports will include the date and time of onset, severity and duration of the event, the relationship to study treatment, the treatment given, and the eventual outcome.

15.B. Definitions

Definitions associated with reportable events can be found on the FHCRC IRO extranet website. (Relevant FHCRC policies include, but are not limited the documents listed **[Table 6]**. Please also refer to the FHCRC IRO website.)

Table 6. FHCRC IRB policies for reportable events

IRB Policy 2.6	Adverse Events and Other Unanticipated Problems Involving Risks to Subjects or Others	http://extranet.fhcrc.org/EN/sections/iro/irb/ae.html
IRB Policy 1.9	Noncompliance with the Office of the Director's Human Research Protection Program Policy	http://extranet.fhcrc.org/EN/sections/iro/irb/ae.html
IRB Policy 1.1	Reporting Obligations for Principal Investigators	http://extranet.fhcrc.org/EN/sections/iro/irb/policy/index.html
IRB Policy 2.2	Continuing Review	http://extranet.fhcrc.org/EN/sections/iro/irb/policy/index.html
IRB Policy 1.13	Investigational New Drugs (IND), Biologics and Investigational Device Exemptions (IDE)	http://extranet.fhcrc.org/EN/sections/iro/irb/policy/index.html

16. DATA AND SAFETY MONITORING PLAN

16.A. Primary Monitoring

The PI of the study will have primary responsibility for ensuring that the protocol is conducted as approved by the Scientific Review Committee and IRB. The PI will ensure that the monitoring plan is followed, that all data required for oversight of monitoring are accurately reported to the Protocol Office and Data Safety Monitoring Board (DSMB), that all AEs are reported according to protocol guidelines, and that any AEs reflecting patient safety concerns are appropriately reported.

16.B. Monitoring Plan

The PI, or a co-investigator on the study designated by the PI, will personally review with the Study Nurse the clinical course of all MCPyV TAg-specific T-cell infusions. The PI or his/her designee will review with the Study Nurse the progress of each patient undergoing therapy as well as the clinical course of all patients who have completed a course of Tcell therapy.

16.C. Monitoring the Progress of the Trial and the Safety of Participants

The FHCRC PI is responsible for monitoring this clinical trial, with oversight by a DSMB, the Protocol and Data Monitoring Committee (PDMC) at the FHCRC, and the FHCRC IRB. This is a phase I/II study and the assessment of risk is considered above minimal.

A DSMB will be in place and will meet after four patients on Group 2 have received treatment (or sooner if requested) to review the data as it relates to AEs and response to treatment. The purpose of the DSMB meetings is to review the conduct of the trial to date and assess safety and toxicity of the study intervention. The DSMB will review all grade III or greater NIH CTC v4.0 toxicities and SAEs and determine whether the study should be prematurely discontinued due to excessive toxicity consistent with **Section 13.B.** Ad hoc meetings may be scheduled as needed.

A report from the DSMB will be submitted to the Coordinating Center IRB (FHCRC) and the PI. The DSMB will discontinue the review of outcomes when all subjects on this trial have completed all protocol-specified follow-up. The DSMB for this study will be composed of Drs. [name], [name], and [name] (**Table 7**).

Table 7. DSMB Members

Name	Affiliation	Position
[name]	FHCRC	DSMB Chair
[name]	FHCRC	DSMB Biostatistician
[name]	University of Washington	DSMB Clinical Investigator

All members have experience in the management of patients with skin cancers and in the conduct and monitoring of clinical trials. Any DSMB member who has or develops a significant conflict of interest will be required to resign from the DSMB. DSMB membership is for the duration of the clinical trial. If any members leave the DSMB during the course of the trial, the PI will promptly appoint their replacement.

A monitor will be retained to monitor study progress. The scope of monitoring will be based on the FHCRC/UW Data and Safety Monitoring Plan (DSMP): <http://www.cancerconsortium.org/rto/prr/DSMPlan.pdf>. Per the DSMP, an initial monitoring visit is expected after the first 4 patients have received treatment with 100% of records verification. Monitoring reports will be forwarded to the DSMB, the IND sponsor, and the PI at FHCRC.

Content of Reports for the DSMB:

- Study number and title. Brief summary of the study design
- Protocol amendments
- Status of accrual. If accrual is slower than expected, a plan for increasing enrollment
- Compliance
- Analyses of primary and secondary endpoints
- Analyses of AEs and overall safety data. A listing of SAEs by subject and by body system
- Analysis of lab values

DSMB Meeting Minutes

The CTSO will provide staff to assist with minutes for the DSMB meeting. The FHCRC IRB and Regulatory Affairs Manager will be included on the distribution list. At the time of IRB annual renewal, DSMB minutes will be required, if not already provided.

Statistical Monitoring Guidelines

The DSMB will review all Grade 3 or greater toxicities as defined by version 4.0 of NCI Common Toxicity Criteria and determine whether the study should be prematurely discontinued due to toxicity. Toxicity grading will be evaluated by the clinical investigators. Criteria for discontinuing of therapy in an individual patient are described in protocol section titled "Management of Toxicities and Complications". Criteria for discontinuing the trial is described in section titled "Data and Safety Monitoring".

The type and grade of toxicities noted during therapy will be summarized for each dose level. All AEs noted by the investigator will be tabulated according to the affected body system. Descriptive statistics will be used to summarize changes from baseline in clinical laboratory parameters. Tumor responses will be determined as specified above.

